#### **Intake and Enrollment Meeting, Part I**

The first part of the Intake and Enrollment meeting will last 60 minutes. During the meeting, the case manager will (a) present a detailed program description and obtain voluntary, informed written consent for program participation from both partners; (b) conduct a formal assessment of domestic violence with each partner individually for 10 minutes (see Domestic Violence Protocol section and Domestic Violence Protocol in the Attachments); (c) enroll participants and collect contact information in nFORM; (d) assign couples to intervention or control group through an automated system of randomization that uses only state of residence (Maryland or Virginia) (PTS); (f) provide orientation about program procedures (one orientation for intervention couples and one orientation for control couples, participants will be given the "Welcome Letter and Instructions for Intervention Couples" or the "Welcome Letter and Instructions for Control Couples" and the "Control Group Flowchart for Participants" or "Intervention Group Flowchart for Participants" - See attachments); (g) describe participants with detailed explanation about payment procedures and VT and MD Tax requirements (providing VT and MD Tax requirements letters in attachmetns; and (h) direct and assist intervention and control couples to complete applicant characteristics survey nFORM and demographic information survey in a tablet (please see grant requirements regarding nFORM collection system)

#### **Intake and Enrollment, Part II**

The second part of the Intake and Enrollment meeting is different for intervention and control couples. For intervention couples (90 minutes; at VT, UMD, FSI, or by phone), the case manager will (a) provide an in-depth description of the study procedure (this will be supported by presenting couples with The Intervention Group Flowchart for Participants to enhance understanding – see this document in Attachments); (b) conduct a Needs Assessment in areas such as health care, employment, housing, childcare, education, legal barrier, income and financial, transportation, food, relationships, mental health, alcohol abuse, and substance abuse in order to determine which areas the couple needs support (see Needs Assessment document in Attachments); (c) schedule the individual and couple development plan (ICDP) meeting, progress meetings, and exit meeting as part of case management; (d) enroll couple in the eight-week TOGETHER workshop (20 hours; at VT, UMD, FSI or designated agencies/schools/churches) and a booster session which occurs three months after the completion of the TOGETHER workshop (3 hours; at VT or FSI); and (e) describe child care support and provide participants with the Child Care Support Letter (see attachments); and (e) explain the media release form and collect participants' signatures for those that agree to have their statements regarding the evaluation of the program be used in the media anonymously to advertise the program. The Schedule for Intervention Couples does not only indicate when and where the scheduled meetings and workshops take place, but also includes the incentives that couples may receive and the content of the meetings. All of these materials are included in the attachments. For intervention couples that do not wish to stay for the 90 minutes of the second part of the Intake and Enrollment meeting, the case manage will offer to conduct the Needs Assessment by phone with both partners at a later time that is agreed upon this meeting. At the end of the meeting the couples is compensated wtih \$40 (\$20/partner) in gift cards for participating in the Needs Assessment.

During part II for control couples, (90 minutes), the case manager will (a) provide a detailed description of the procedure for control group (this will be supported by presenting couples with The Control Group Flowchart for Participants to enhance understanding – see this document in Attachments); (b) oversee and assist couples complete pre-test surveys including the Pre-Program Survey (nFORM) and Pre-test Assessment (Qualtrics) (both surveys combined will take about 90 minutes – For content of assessments please see documents Pre-Program Survey nForm and Pre-Test Assessment in Attachments; (c) provide the couple their compensation in gift cards \$40 per couple (\$20/partner) for assessments; (d) ask partners to sign the Gift Card Receipt (see document in Attachments) after receiving the gift cards; and (e) schedule the couple for their post-test assessment meeting (in 8 weeks) and financial workshop/follow-up assessment (six months from the date of the post-test assessment meeting months). In the event that control couples cannot stay for this second part of the Intake and Enrollment meeting, they will be offered the possibility of completing the pre-program survey nForm and pre-test assessment in paper format or online. If the couple chooses to complete the survey and assessment in paper, they will be provided the questionnaires, the instructions to complete the questionnaire, and a self-addressed envelope to mail the questionnaires. The instructions will explain that they will be mailed the gift cards once the questionnaires are received and that they will be required to fill out a Gift Card Receipt (see document in Attachments). If the option is available and couples agree to it, they may receive the gift cards electronically once we have received the mailed questionnaires. If the couple chooses to complete the survey and pre-assessment online, we will be emailing to each partner the link and the individual passcode and we will be mailing the gift cards or provide them electronically, if this option is available and the couple agrees to it, once they complete the questionnaires.

#### **CONTROL COUPLES**

##### **Control Couples: Post-Test Assessment Meeting**

Eight weeks after the Intake and Enrollment meeting, control couples will return to, VT, UMD, FSI or designated locations to meet with the case manager, and complete the Post Program Survey in nFORM and the Post-test Assessment in Qualtrics (both surveys combined will take about 90 minutes). ) The case manager will provide the couple their compensation in gift cards \$40 per couple (\$20/partner) for assessments and ask partners to sign the Gift Card Receipt Form (see document in Attachments) after receiving the gift cards.. Couples will be reminded about Financial Literacy Workshop (FLW) and follow-up assessment date. For couples that cannot attend the meeting in person, the questionnaires will be mailed to them with instructions on how to complete them and return them to the program in a self-addressed envelope included in the package (see Letter and Instructions for Post-Test Survey for Control Couples document and Post-Test Survey document (Post-Program Survey nFORM + Post-Test Assessment) in Attachment. Upon receipt of questionnaires by program staff, the gift cards and Gift Card Receipt Form will be mailed to the couple with instructions to complete the form and mail it back to the program staff in the self-addressed envelope provided (see Letter and Instructions for Completion Gift Card Receipt Form in Attachments). If electronic gift cards are available and couples choose this option, the card will be emailed upon receipt of the questionnaires. Couples may also choose to complete the post-survey and post-assessment online, in which case we will be emailing to each partner the link and their individual passcode and we will be mailing the gift cards or provide them electronically, if this option is available and the couple agrees to it, once they complete the questionnaires

##### **Control Couples: Follow-Up Survey/Financial Literacy Workshop**

Six months after control couples will be invited to come 90 minutes before the Financial Literacy Workshop that will be offered for them. Trained program staff will provide tablets for these couples to complete the follow-up survey in Qualtrics before the beginning of the workshop. Completion of follow-up survey will take about 90 minutes. The trained program staff will provide the couple their compensation in gift cards \$80 per couple (\$40/partner) for assessments and will ask partners to sign the Gift Card Receipt Form. After the participants complete the follow-up survey, they will be invited to attend a three-hour Financial Literacy Workshop (FLW), led by

workshop facilitators at VT, UMD, FSI or designated locations. FLW is a three-hour financial management class to improve financial management knowledge and skills based on Money Smart curriculum by the Federal Deposit Insurance Corporation.

For couples that cannot attend the meeting in person, the questionnaires will be mailed to them with instructions on how to complete them and return them to the program in a self-addressed envelope included in the package (see Instructions for Mailed Follow-up Survey in Attachments). Upon receipt of questionnaires by program staff, the gift cards and Gift Card Receipt Form will be mailed to the couple with instructions to complete the form and mail it back to the program staff in the self-addressed envelope provided (see Letter and Instructions for Completion of Gift Card Receipt Form in Attachments). Couples may also choose to complete the follow-up survey online in which case we will be emailing to each partner the link and their individual passcode and we will be mailing the gift cards or provide them electronically, if this option is available and the couple agrees to it, once they complete the questionnaires.

#### **INTERVENTION COUPLES**

##### **Intervention Couples: ICDP meeting**

Within two weeks of the Intake and Enrollment meeting, intervention couples will partake in an Individual and Couple Development Plan (ICDP) meeting with the assigned case manager at VT, FSI, UMD, or designated locations for 90 minutes. Based on the information collected in the Needs Assessment during the IE meeting, the case manager will create an Individual and Couple Development Plan with the couple that will include (a) setting individual and couple goals; (b) agreeing on action steps and establishing a realistic timeline to meet those goals; (c) discussing possible barriers participants might encounter; (d) providing referrals as part of the action steps to meet their goals (i.e., housing, TANF, health care, child welfare, child support services, mental health services, and job and career enhancement services). See the Individual and Couple Development Plan Form in Attachments. At the end of this meeting participants will be reminded of all of their scheduled appointments. If the ICDP includes a goal within the area of employment/career a first meeting will be scheduled for the partner in need of those services with an employment case manager to receive services at either the SkillSource Group, Inc. or a federally funded employment agency in Maryland depending on where the participant receives services in our program. In addition, the participant will be invited to sign a release to exchange information between the employment agency and our program so that information can be exchanged with the employment agency regarding information collected by our program (Couple's Needs Assessment and the Individual and Couple Development Plan) and the employment agency (employment/career services recommended and received, the participant's eligibility for those services, and the Employment Individual Plan). The signature of this release is necessary for the integration and coordination of services that are part of the present study.

However, once the participant is referred to the employment agency, he/she becomes their participant and they are obliged to maintain confidentiality about their participants' information.

The present study provides funding for (a) employment services for those participants that do not meet eligibility criteria to receive services funded through the Workforce Innovation and Opportunity Act (WIOA) or other state and local funding in those agencies and (b) for reporting all the employment/career services that participants referred from our program are recommended (Individual Employment Plan) and actually receive (Employment Services and Trainings Tracking Form) in such agencies. Since this study targets the low-income population, it is expected that most participants will meet eligibility criteria to receive services in those agencies funded through WIOA or state or local programs and not through this study. The Release to Exchange Information with Employment Agency is also necessary because the case manager will be sharing the needs' assessment and the ICDP and both documents relate to both partners and not just the one that may be receiving services at the employment agency. Therefore, both partners' consents are required to share those documents with the employment agency. Sharing these documents will allow the employment case manager to see what other referrals have been made for the couple. This is important information to avoid duplication of services as the employment agencies also have needs assessments and make referrals based on the individual's needs (see the Release to Exchange Information with Employment Agencies in Attachments, the Individual Employment Plan, Employment Services and Trainings Tracking Form, and the WIOA Eligibility Form). In

addition to paying for employment/ career services for participants that do not meet the eligibility criteria of for federally, state, or local funded employment programs, the current study provides funding for two employment case managers, one for VA and one for MD. VA participants in need of employment services will be referred to an employment case manager working at SkillSource, Inc. MD participants in need of employment services will be referred to an employment case manager hired by UMD or FSI. that will assist participants in getting services (individual employment assessment and plan, trainings, and services) in WOIA employment agencies in Maryland. Employment case managers at VA and MD will be responsible for developing and/or collecting the individual employment assessment and plan and tracking all employment trainings and services that each participant receives). Even though it is desirable that both partners attend this ICDP meeting in person, the option will be giving to attend it by phone if partners can't attend in person. If partners choose to attend it by phone, the gift cards will be mailed to their home or emailed if this option is available.

#### **Intervention Couples: TOGETHER Workshop**

Couples will begin the TOGETHER workshop at UMD, VT, FSI, or designated agencies, schools, or churches. TOGETHER is a 20-hour psychoeducational program for couples that supports the personal wellbeing, couple relationship, parenting, and financial literacy and management.

TOGETHER was developed by [name] (PI) and the late [name] as part of the emerging interdisciplinary field that integrates relationship education with financial education (Falconier, 2015). TOGETHER adapted the Couples' Coping Enhancement Training (CCET) program developed by [name] (Bodenmann, 1997) and whose effectiveness in improving stress management, communication, and relationship satisfaction has been supported in various studies (Bodenmann & Shantinath, 2004; Lederman, Bodenmann, & Cina, 2007; Shaer, Bodenmann, & Klink, 2008) to financially distressed couples by applying CCET content to financial issues and incorporating financial education. The workshop aims at reducing financial stress and improving relationship functioning by providing couples with knowledge and skills on stress management, communication, conflict resolution and management, problem-solving, and financial management.

The TOGETHER workshop has 9 modules and is designed to be delivered in groups of four to eight couples for 20 hours: 8 weekly sessions of 2.5 hours each. Each session is co-led by two facilitators: a financial counselor and a couples therapist. Each session includes a warm-up activity, brief review of past session content and homework, presentation and practice of new content, summary of all contents covered in the session, and assignment of new homework. After each session, couples are assigned homework so that the skills learned in the session can be practiced between sessions. The TOGETHER curriculum has been pilot tested and results have been published in 2015 in the Journal of Marital and Family Therapy. FSI and TWC will hire couple therapists and financial counselors to provide these workshops. Couple therapists and financial counselors will be trained by [name] and [name].

The TOGETHER workshop will be offered at FSI, UMD, VT, or designated agencies, schools, or churches. There will be eight offerings in each facility per year. The workshop will be offered in eight sessions (2 hours and 30 minutes each) scheduled on the same day of the week and at the same time. Efforts will be made to offer the sessions in the evenings and on weekends to facilitate participation. Participants complete a 2 minute-session evaluation and a 2-minute homework evaluation within the time allotted to the session. In the last session they complete a 5 minute session evaluation+overall workshop evaluation within the session (see Session Evaluation questionnaire, homework evaluation questionnaire, and session evaluation and overall workshop evaluation questionnaire).

At the first TOGETHER session, couples will complete the Pre Program Survey (nFORM) and the Pre-test Assessment (Qualtrics) before the session begins. Completion of the Pre Program Survey and Pre-test Assessment will take about 90 minutes. For participants both surveys will be collectively referred to as "Pre-Test Survey". Partners will be instructed to complete these surveys in tablets provided by the group facilitators. Couples will receive compensations for

completing assessments in gift cards \$40 per couple (\$20/partner) and each partner will be required to sign and date the Gift Card Receipt Form upon receipt of the gift cards. TOGETHER session facilitators will oversee the completion of the Pre-Test Survey. Participants that fail to attend the first session of the TOGETHER workshop will be mailed the Pre-Test Survey for their completion (see in attachments these two documents: Instructions for Completion of Mailed Pre-Test Survey for Intervention Couples and the Pre-Test Survey (that shows the paper and pencil format for these two surveys combined: Pre-test Assessment and Pre-Program Survey). Participants will be instructed to return the completed surveys on the second session to receive their gift cards. Couples that wish to complete the pre-test survey online instead will be instructed on how to do so.

After the last (eighth) TOGETHER session, couples will start at either FSI, UMD, VT, or designated agencies to complete the Post Program Survey (nFORM) and the Post-test Assessment (Qualtrics). Surveys will take about 90 minutes. Participants will know these surveys as Post-Test Surveys and will complete them in the tablets. Couples will receive compensations for completing assessments in gift cards \$40 per couple (\$20/partner) and each partner will be required to sign and date the Gift Card Receipt Form upon receipt of the gift cards. TOGETHER session facilitators will oversee the completion of the Post-Test survey. Participants that fail to attend the eighth session of the TOGETHER workshop will be mailed the questionnaires with instructions on how to complete them and be given the gift cards (see in Attachments two documents: Instructions for Completion of Mailed Post-Test Survey for Intervention Couples in Attachments and the Post-Test Survey (that includes both surveys, the Post-Program Survey in nFORM and the Post-Assessment in Qualtrix). Couples that wish to complete the post-test survey online instead will be instructed on how to do so.

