The project employs a randomized control trial (RCT), in which 360 couples are assigned to the intervention group and 360 couples to a control group between June 1, 2016 and September 30, 2020. Our approach integrates three components (1) a 20-hour evidence-informed couple group program called TOGETHER workshop that integrates relationship education and financial literacy skills, (2) case management (assessment of participant needs, development of Individual and Couple Development Plan, referrals for social and mental health services, and referrals and coordination with job and career enhancement services, linking and coordination of all services as needed), and (3) job and career enhancement services for those who need the services.

The main goals of this project are to promote healthy couple relationships and economic stability and mobility for low-income couples in Northern Virginia, Prince [name], and [name]. The main objectives are: 1) improve personal wellbeing; 2) improve

**couple's relationship skills; 3) improve parenting and co-parenting; 4) improve financial literacy and capability; and 5) improve employability, job placement, and retention skills.**

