**Target population in the proposed project is low-income couples, but any couple that wants to participate in the program will be accepted as long as they meet the eligibility criteria: residing in Northern Virginia and Prince George's County and Montgomery County in Maryland, married or cohabiting for at least a year, 18 years of age or older, and English-speaking. Exclusion criteria includes both partners being retired, physical domestic violence (defined as behaviors that frighten, terrorize, manipulate, hurt, humiliate, blame, often injure, and sometime kill, a current or former intimate partner) or feeling unsafe with partner in the last six months, current diagnosis of a severe psychiatric disorder that required hospitalization in the last 12 months, cognitive impairment, or/and severe untreated substance abuse disorder. Couples can participate as long as both partners consent to be part of the program.**

**To conduct the randomized control trial, 360 couples will be enrolled (180 from Northern Virginia and 180 from Montgomery County, Maryland) for the intervention group and 360 couples (180 from Northern Virginia and 180 from Montgomery County, Maryland) for the control group. Within each group (intervention and control), 20 couples will be enrolled in Year 1 (7/1/16-9/30/16), 100 in Year 2 (10/1/16-9/30/17), and 100 Year 3(10/1/17-9/30/18), 100 in Year 4 (10/1/18-9/30/19), and 40 in Year 5 (10/1/19-9/30/20).**

**Recruitment activities will begin on June 1, 2016. Activities will include producing and distributing flyers, brochures, and posters and/or giving presentation in schools, churches, faith-based community centers, child support agencies, TANF offices, WIC agencies, Head Start programs, Healthy Start program, child welfare agencies, community centers, libraries, stores, barber shops, employment centers, Virginia Tech and University of Maryland clinics and cooperative extension centers, and community events. The Women's Center and Family Services Inc. will concentrate on marketing and recruitment efforts from the network of providers and partner organization they are part of. In addition, graduate students will be responsible for setting up social media outlets that will be used for marketing and recruitment purposes and posting calendars with program activities. The program will also be advertised through its own website ([www.togetherprogram.org](http://www.togetherprogram.org)) and online ads.**

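### The pre-test follows assignment and is taken at different points in the two arms, yet the SAP constrains baseline means to equality: a risk for the full-programme effect, of unknown size and direction

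*Protocol*

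**What the plan says.** The protocol's opening section randomizes couples to a three-component programme. Besides the workshop and employment services it includes "case management (assessment of participant needs, development of Individual and Couple Development Plan, referrals for social and mental health services" and related coordination.

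In Intake and Enrollment Meeting, Part I, the case manager is to "assign couples to intervention or control group through an automated system of randomization that uses only state of residence" and then to "direct and assist intervention and control couples to complete applicant characteristics survey nFORM and demographic information survey in a tablet". Assignment therefore precedes every outcome survey in both arms.

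Part II differs by arm. For control couples the case manager is to "oversee and assist couples complete pre-test surveys including the Pre-Program Survey (nFORM) and Pre-test Assessment (Qualtrics"; if they cannot stay, "they will be offered the possibility of completing the pre-program survey nForm and pre-test assessment in paper format or online". For intervention couples Part II holds the Needs Assessment; if they do not stay, "the case manage will offer to conduct the Needs Assessment by phone with both partners at a later time". The section on the ICDP meeting (Individual and Couple Development Plan) places that meeting, with goals and referrals, within two weeks of intake. The workshop section then says: "At the first TOGETHER session, couples will complete the Pre Program Survey (nFORM) and the Pre-test Assessment (Qualtrics) before the session begins". Couples who miss session 1 return a mailed survey at session 2, and an online option exists. No section dates session 1 relative to intake.

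The SAP's Data Analysis Plan
- defines the intervention period as pre-test to post-test;
- codes time as months between assessments;
- constrains the two groups' baselines to equality (constrained longitudinal data analysis);
- controls for baseline outcomes in all analyses;
- plans a baseline-equivalence comparison, which for the entire sample it describes as being at initial randomization.

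**The concern.** Equal baseline means in expectation are a consequence of randomization only when the baseline measure cannot be affected by assignment. Here the timing, the setting and the prior exposure at pre-test all depend on the arm. If early case management, or change over the wait, shifts the intervention pre-test, the constrained model reads that shift as chance imbalance and removes part of it from the estimated effect. The SAP's time variable does not help, because it measures intervals between assessments and not the time from assignment to pre-test. Since every planned analysis uses the pre-test, none would show the full-programme effect free of this assumption.

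**Working it through.** The documents give no SD, correlation, power or dropout figure, so there is no stated result to reproduce. The order of events comes from the documents; the statistical inputs below are assumptions.

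**1. Timetable in weeks from assignment (W = undated wait to session 1, default route)**

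| Event | Control | Intervention |
|---|---|---|
| Needs Assessment | none | 0 (or a later phone call) |
| ICDP meeting | none | by week 2 |
| Pre-test | 0 | W |
| Post-test | 8 | W + 7 (eight weekly sessions) |

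Time from assignment to post-test differs between arms by (W + 7) - 8 = W - 1 weeks.

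**2. How long is W?** These are illustrations only.
- Eight offerings per facility per year: 52/8 = 6.5 weeks between starts. With intakes spread evenly and couples taking the next start, the mean wait is 3.25 weeks, and 1 - 2/6.5 = 69% wait past the two-week ICDP limit.
- Enrolment plan (per arm): "20 couples will be enrolled in Year 1 (7/1/16-9/30/16), 100 in Year 2 (10/1/16-9/30/17". Take 100 intervention couples a year, half in each state, in groups of at least four. That allows at most 50/4 = 12.5 starts per state, one per 52/12.5 = 4.16 weeks. The mean wait is 2.1 weeks, and 1 - 2/4.16 = 52% wait past two weeks.
- If a start in either state is usable: 25 starts, one per 2.08 weeks. The mean wait is about 1 week, and 1 - 2/2.08 = 4% wait past two weeks.
- Check against Progress Meetings and Exit Meeting. Put the ICDP at its latest (week 2), the first gap at 5 weeks, the next five gaps at g weeks each, and six months at 26 weeks. Then session 1 = 2 + 5 + 5g - 26 - 7 = 5g - 26. With g = 5 this is week -1, with g = 5.2 week 0, and with g = 5.6 week 2. The intervals are stated as approximate, so they suggest a short wait without fixing it. These sections need reconciling with the date of session 1.

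**3. Effect of a pre-test shift on the constrained model.** Assumptions: couple means, complete data, 360 couples per arm, total variance 1, within-person correlation rho = 0.5 to 0.7, partner correlation c = 0.1 to 0.4.
- Variance of a couple mean: V = (1 + c)/2. Covariance across occasions: C = (rho + c)/2. Slope: beta = C/V = (rho + c)/(1 + c).
- Bias = -beta x delta.
- SE with the pre-test = sqrt[(2/360)(V - C²/V)]. SE without it = sqrt[(2/360)V].

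| rho, c | beta | SE with | SE without | Ratio |
|---|---|---|---|---|
| 0.5, 0.1 | 0.545 | 0.0463 | 0.0553 | 1.19 |
| 0.6, 0.2 | 0.667 | 0.0430 | 0.0577 | 1.34 |
| 0.7, 0.4 | 0.786 | 0.0386 | 0.0624 | 1.62 |

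A shift of 0.05 SD moves the estimate by -0.027 to -0.039; 0.10 SD by -0.055 to -0.079; 0.20 SD by -0.11 to -0.16. The main model's 95% half-width over the grid is 0.074 (rho 0.7, c 0.1) to 0.094 SD (rho 0.5, c 0.4). A separate two-wave simulation (rho 0.7, shift 0.10) gave -0.069 against -0.070 by formula; with no shift it gave -0.001.

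**4. Would the planned baseline comparison show it?** If tested two-sided at 5% on one outcome, it flags a 0.05 SD shift 13 to 15% of the time, 0.10 SD 36 to 44%, and 0.20 SD 89 to 95%.

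**5. Three origins of the same 0.10 SD shift (rho 0.6, c 0.2, no workshop effect)**

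| Origin | True effect from assignment | With pre-test | Without pre-test |
|---|---|---|---|
| Early effect, fades | 0 | -0.067 | 0.000 |
| Early effect, persists | 0.10 | 0.033 | 0.100 |
| Stable difference from selective completion | 0 | 0.033 | 0.100 |

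The last two rows give identical estimates. For an early effect, the model without the pre-test is right. For selection, it carries the full 0.10 error, while conditioning on the pre-test removes most of it.

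**The case against.** The strongest defence is that the SAP expects better outcomes on completion of the workshop and runs its intervention period from pre-test to post-test. Session 1 is then the natural baseline. That stands for the workshop alone. It does not settle the three-component programme to which couples were randomized, and the SAP states its main goal simply as the effectiveness of the intervention.

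A second defence is that the wait may be short and the exposure slight. If W is near zero, the only default prior contact is the Needs Assessment, which identifies areas of need; goals and referrals come at the ICDP. Nothing in the documents supports any particular delta. This stands too. A reader might infer that the ICDP usually precedes the intervention pre-test, but an illustrative range of 4 to 69% does not show that.

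A third concerns the remedy. With complete data, the estimate without the pre-test minus the estimate with it equals beta times the observed baseline difference. The extra model therefore adds little to the baseline comparison already planned, and it cannot tell early effect from selection or chance. That limits its role but leaves it useful: it puts the full-programme contrast on the outcome scale with its own interval.

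A reader might also infer that selective completion of the pre-test biases the main model by the same -beta x delta. It does not: a stable selection difference is partly corrected by conditioning.

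**Conclusion.** The concern holds as a limit on what the main model estimates. Both pre-tests follow assignment, they are taken at arm-specific points, and the equality constraint is not secured by randomization for the full programme. An early treatment effect, or change over the wait, of delta moves the estimate by about -0.55 to -0.79 times delta. For 0.10 SD that is -0.055 to -0.079 SD, of the same order as the model's 95% half-width. The multipliers rest on assumed correlations and complete data, and delta itself is unknown in size and sign.

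The documents do not support saying that the reported effect is too small, or too large, or that the workshop effect is compromised. The planned baseline comparison is a partial check: it would probably reveal a 0.20 SD shift but more often than not miss a 0.10 SD one, and a shift it finds is still not corrected by the constraint.

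**What to change.** **Data already collected.** Planned enrolment ended 9/30/20 and the SAP revision is dated 11/18/2021, so this is the part most likely to apply.
1. Report by arm the dates of assignment, Needs Assessment, ICDP meeting, pre-test and post-test, and the pre-test missingness.
2. State that the main model's effect runs from the pre-test, by default session 1 in the intervention arm, and not from assignment.
3. Add one sensitivity model comparing post-test and follow-up by arm without the pre-test, adjusted for the demographics both arms give in Intake Part I. Present it beside the main model and the baseline comparison, as addressing early treatment effects only and not as a replacement.

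The cost is some tabulation and one model. Its 95% half-width is 0.108 to 0.122 SD, 19 to 62% wider than the main model under the assumptions above. It is worse under selective completion, does not correct differential dropout, and compares arms at 8 versus W + 7 weeks from assignment. Change scores or arm-specific baselines are not a remedy, because they carry the full shift (-delta).

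**Any couples still to be enrolled.** Give both arms the same pre-test at intake, with one common paper or online fallback and recorded completion dates. Do this before assignment if identifiers allow (Case Intake Information opens the nFORM file only after randomization), otherwise at the start of Part II before the Needs Assessment. In one sitting the intervention intake could reach 60 + 90 + 90 = 240 minutes, less if the Needs Assessment is moved to the existing phone option. Total burden is unchanged, since the 90 minutes leave session 1.
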